6.12.2 Primary Endpoint

The primary endpoint is the change from baseline to Week 12 in average daily hours of ON-time without troublesome dyskinesia with mesdopetam compared to placebo as assessed with 24-hour patient home diaries.

The hypothesis that will be tested is as follows:

 $H_0 = \mu_{mesdopetam} - \mu_{placebo} = 0$ versus $H_1 = \mu_{mesdopetam} - \mu_{placebo} \neq 0$

Where $\mu_{mesdopetam}$ denotes the mean change from baseline to Week 12 in the mesdopetam treatment group (2.5 mg b.i.d., 5 mg b.i.d., or 7.5 mg b.i.d.), and $\mu_{placebo}$ denotes the mean change from baseline to Week 12 in the placebo group.

The null hypothesis is that there is no difference between mesdopetam and placebo for the primary efficacy endpoint and the alternative hypothesis is that there is a difference between mesdopetam and placebo for the primary efficacy endpoint.

6.12.3 Primary Analysis

The number and percent of patients with valid diaries will be tabulated by treatment group and visit and a listing of diary completion will be provided. Descriptive statistics for the actual values by visit (including baseline) and change from baseline to each post-baseline visit (Visits 3, 4 and 5/EOT) in average daily ON-time without troublesome dyskinesia (hours) will be presented.

Change from baseline in average daily ON-time without troublesome dyskinesia (hours) will be analysed using a mixed model for repeated measures (MMRM) for all patients in the FAS. Change from baseline to Week 12 is the timepoint of interest for this analysis. Any missing data is assumed to be missing at random (MAR) for this analysis.

The model will include randomized treatment (2.5 mg, 5.0 mg, 7.5 mg, or placebo b.i.d.), visit, country, and treatment by visit interaction as explanatory, fixed effect variables. Country will be

Worldwide Clinical Trials Controlled Quality Management Document		
WORLDWIDE CLINICAL TRIALS	Sponsor:	Integrative Research Laboratories Sweden AB
	Protocol Number:	IRL790C005
STATISTICAL ANALYSIS PLAN. PHASE 2-3-4		

weighted by the number of patients participating from each county. Baseline value for average daily hours of ON time without troublesome dyskinesia will be included as a continuous covariate along with the randomisation stratification factor of daily hours spent in ON-time with troublesome dyskinesia (<6 hours, \geq 6 hours).

An unstructured covariance matrix will be assumed for within-patient correlation over time. If the model fails to converge, the first approach for which the model converges among the following will be used: banded Toeplitz (TOEP), compound symmetry (CS) and variance component (VC).

The LS mean estimate, corresponding SE, and 95% CI for the change from baseline at each postbaseline visit will be obtained from the model and presented for each treatment group. The estimated treatment difference for each dose level compared to placebo and the combined dose levels compared to placebo, the corresponding SE, and p-value will also be presented by visit.

A line plot showing the LS mean ($\pm 95\%$ CI) change from baseline at each visit for each treatment group will also be provided.

The following is the sample SAS code that will be used for this analysis:

```
PROC MIXED DATA= analysis (where = (avisitn ne 0));
    ODS OUTPUT LSMeans=LSMeans Diffs=Diffs LSMEstimates=Estimates;
    CLASS USUBJID STRATF TRT01PN AVISITN COUNTRY;
   MODEL CHG = BASE STRATF TRT01PN AVISITN COUNTRY TRT01PN*AVISITN / DDFM=KR
s;
    REPEATED AVISITN / SUBJECT=USUBJID TYPE=UN;
    LSMEANS TRT01PN*AVISITN / CL DIFF OM;
    LSMESTIMATE TRT01PN*AVISITN 'Difference at Week 4' 1 0 0 1 0 0 1 0 0 -3 0
0 divisor = 3 / CL e OM;
    LSMESTIMATE TRT01PN*AVISITN 'Combined at Week 4' 1 0 0 1 0 0 1 0 0 0 0 0
divisor = 3 / CL e OM;
    LSMESTIMATE TRT01PN*AVISITN 'Placebo at Week 4' 0 0 0 0 0 0 0 0 0 3 0 0
divisor = 3 / CL e OM;
    LSMESTIMATE TRT01PN*AVISITN 'Difference at Week 8' 0 1 0 0 1 0 0 1 0 0 -3
0 divisor = 3 / CL e OM;
    LSMESTIMATE TRT01PN*AVISITN 'Combined at Week 8' 0 1 0 0 1 0 0 1 0 0 0 0
divisor = 3 / CL e OM;
    LSMESTIMATE TRT01PN*AVISITN 'Placebo at Week 8' 0 0 0 0 0 0 0 0 0 0 3 0
divisor = 3 / CL e OM;
    LSMESTIMATE TRT01PN*AVISITN 'Difference at Week 12' 0 0 1 0 0 1 0 0 1 0 0
-3 divisor = 3 / CL e OM;
```

QMD Ref: Worldwide-TMP-ST-005-7.0 Effective: 12Aug2019	Governing QMD: Worldwide-SOP-ST-001	
Confidentiality Statement		
This document is the property of Worldwide Clinical Trials Inc. and may not be duplicated, copied, altered or removed from company without prior approval from Worldwide Quality Assurance or in compliance with Worldwide Standard Operating Procedures.		

REF: Worldwide-TMP-QA-001f-1.3

Worldwide Clinical Trials Controlled Quality Management Document		
WORLDWIDE CLINICAL TRIALS	Sponsor:	Integrative Research Laboratories Sweden AB
	Protocol Number:	IRL790C005
STATISTICAL ANALYSIS PLAN. PHASE 2-3-4		

RUN;

Where USUBJID = Subject Number; TRT01PN = Planned Treatment Group Number; AVISITN = Visit Number; BASE = Baseline Value; CHG = Change from Baseline Value; COUNTRY = Country; STRATF = Stratification Factor.

6.12.4 Sensitivity Analyses

6.12.4.1 Pattern-Mixture Model

To assess the robustness of the results to deviations from the MAR assumption in the primary analysis, a sensitivity analysis will be conducted such that non-monotone missing data is imputed under the MAR assumption while the monotone missing data is imputed under the missing not at random (MNAR) assumption (i.e., that missingness is also dependent on the unobserved variable values).

This analysis will therefore provide a stress test of the MAR assumption in the primary analysis and will provide a conservative estimate of the treatment effect.

The pattern-mixture modeling will be implemented by first turning the non-monotone missing data pattern into a monotone missing pattern under the MAR assumption using the Markov Chain Monte Carlo (MCMC) method in SAS' PROC MI with the IMPUTE = MONOTONE and the PRIOR = JEFFREYS options to specify a non-informative prior for the imputation process. Then the MONOTONE statement along with the MNAR statement with option MODEL in SAS' PROC MI will be utilized to implement the MNAR assumptions and control-based pattern imputation^{2,3}. The inference of this sensitivity analysis will be based on the combined estimates using the standard multiple imputation technique via Rubin's⁴ rules.

Missing data will be imputed using a pattern-mixture model approach that uses a control-based pattern imputation. With this approach, patients who discontinued from active treatment groups will be assumed to follow a similar outcome trajectory as patients from the placebo (control) group, and patients who discontinued from placebo (control) group are modeled as completers within their own group (MAR within control group). That is, the imputation model for the missing observations in the active treatment groups is constructed not from the observed data in the active treatment groups, but rather from the observed data in the placebo group. This model is also the

Worldwide Clinical Trials Controlled Quality Management Document		
WORLDWIDE CLINICAL TRIALS	Sponsor:	Integrative Research Laboratories Sweden AB
	Protocol Number:	IRL790C005
STATISTICAL ANALYSIS PLAN. PHASE 2-3-4		

imputation model that will be used to impute missing observations in the placebo group. The missing values for each variable will be imputed based on a model simulated from the posterior predictive distribution of the conditional regression model fitted on the imputed variable using only the observations from the placebo group.

This will be implemented by utilizing the MONOTONE REG statement and MNAR statement with option MODEL of SAS' PROC MI with options nimpute = 20 and seed = 32641726.

The following is the sample SAS code that will be used to implement the control-based pattern mixture imputation:

```
PROC MI DATA=DATAIN OUT=DATAIN_MONO SEED=32641726 NIMPUTE=1;
BY TRT01PN;
VAR BASE ONHOURS3-ONHOURS5;
MCMC CHAIN=MULTIPLE IMPUTE=MONOTONE PRIOR = JEFFREYS;
RUN;
PROC MI DATA= DATAIN_MONO SEED=32641726 NIMPUTE=20
OUT=DATA_IMPUTED;
CLASS TRT01PN STRATF;
MONOTONE REG(BASE ONHOURS3-ONHOURS5);
MNAR MODEL(ONHOURS3-ONHOURS5 / MODELOBS=(TRT01P='Placebo'));
VAR STRATF BASE ONHOURS3-ONHOURS5;
RUN;
```

Once the missing diary data has been imputed for all visits, the change from baseline at each visit will be calculated and consequently will be analysed using the same MMRM model employed in the primary analysis for each iteration of the imputed dataset.

Then the results are to be summarized using PROC MIANALYZE, where the treatment group LS means and their differences between treatments will be combined across all 20 imputed datasets:

```
PROC SORT DATA= LSMEANS; BY TRT01PN AVISITN _IMPUTATION_; RUN;
PROC MIANALYZE DATA= LSMEANS;
MODELEFFECTS ESTIMATE;
STDERR STDERR;
ODS OUTPUT PARAMETERESTIMATES= LSMEANS_COMB;
BY TRT01PN AVISITN;
RUN;
```

QMD Ref: Worldwide-TMP-ST-005-7.0 Effective: 12Aug2019	Governing QMD: Worldwide-SOP-ST-001	
Confidentiality	v Statement	
This document is the property of Worldwide Clinical Trials Inc. and may not be duplicated, copied, altered or removed from company without		
prior approval from Worldwide Quality Assurance or in compl	iance with Worldwide Standard Operating Procedures.	

REF: Worldwide-TMP-QA-001f-1.3

PROC SORT DATA= DIFFS; BY TRT01PN; RUN; PROC MIANALYZE DATA= DIFFS(WHERE=(AVISITN=_AVISITN)); MODELEFFECTS ESTIMATE; STDERR STDERR; ODS OUTPUT PARAMETERESTIMATES= DIFFS_COMB; BY TRT01PN AVISITN; RUN;

LS means, SEs, and 95% CIs for each treatment group based on the imputed data will be presented at each week as well as the estimate of treatment difference, SE, and p-value at each week with Week 12 as the primary timepoint of interest.

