14.2. Sample size/power calculation

140 patients (35 per group), are enough to demonstrate a treatment difference of 3 hours, pooled standard deviation 3.5, between a single dose level of active treatment and control (i.e. 2.5 mg, 5 mg or 7.5 mg mesdopetam vs placebo b.i.d.) for the primary endpoint with 92% power and type 1 error rate 0.05 (two tailed). The sample size calculation is based on an expected dropout rate of 10%. The Sponsor will evaluate the actual dropout rate after 70 randomized patients have completed Visit 3 (week 4) and can, if the dropout rate in the study is higher than expected, decide to increase the sample size to a total of maximum 154 randomized patients (+10%).

Confidential	Version: 5.0	Page 62 of 74
Protocol: IRL790C005	Date: 5 Mar 2021	C

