6.12.4.2 Tipping Point Analysis

If the primary efficacy analysis significantly favours mesdopetam, a tipping-point sensitivity analysis for the primary efficacy endpoint will be conducted on the significant dose groups to investigate how severe the departure from the MAR assumption must be to overturn the conclusion from the primary analysis. In this analysis, the assumption will be that missing data in the active treatment groups follows a MNAR pattern.

A tipping-point approach will be used such that the trajectories of the patients in the active treatment groups after early termination from study are assumed to be worse than placebo by a fixed amount (δ). Missing values will first be imputed using a MAR approach and then the value of δ will be deducted from all imputed values occurring after early termination for patients in the active treatment groups only. The value of δ will be applied in increments of 0.5 hours (i.e., 0.5h, 1h, 1.5h, 2h) up to the point at which the treatment difference at Visit 5 (Week 12) is no longer statistically significant at the local level (see Section 0). This analysis provides a measure of the degree by which the patients in the active treatment groups who discontinued early would need to be worse, compared to patients with similar trajectories up to the point of discontinuation in the same treatment arm, at each post-discontinuation visit for the null hypothesis of no treatment difference to no longer be rejected.

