6.15 Multiplicity

Multiple dose levels have been included in the study design to evaluate the dose-response relationship of mesdopetam with the hypothesis that the 7.5 mg b.i.d. dose will be the most efficacious of the dose levels studied.

Two key secondary endpoints (change from baseline in ON-phase dyskinesia assessed by MDS-UPDRS Question 4.2 and change from baseline in disability associated with ON-phase dyskinesia assessed with the sum score of UDysRS parts 1b and 4) will also be evaluated and thus a strategy for controlling the overall error rate whilst maintaining the planned study power is required.

To such aim, a hierarchical testing strategy will be used whereby first the 7.5 mg b.i.d. will be tested at a 5% level on the primary endpoint, and should the test be significant, the 2 key secondary endpoints will be tested for the 7.5 mg b.i.d. dose using a truncated Hochberg procedure with a truncation parameter $\gamma = 0.7$. This procedure works as follows for n = 2 tests:

- 1) p-values are sorted in ascending order as p_1 and $p_{2;}$
- 2) The largest p-value, p₂, is compared against the modified critical value c₂ below:

$$c_2 = \left[\frac{\gamma}{n-i+1} + \frac{1-\gamma}{n}\right]\alpha = \left[\gamma + \frac{1-\gamma}{2}\right]\alpha = \left[0.7 + \frac{0.3}{2}\right]0.05 = 0.0425$$

(where n = 2 and i = 2)

- 3) If $p_2 \le c_2$ then all key secondary hypotheses are rejected, otherwise the hypothesis associated with p_2 is retained and the other p-value, p_1 , is compared against the critical value c_1 , which can be obtained from the formula in 2) by replacing *i* with 1, leading to a critical value of 0.025;
- 4) If $p_1 \le c_1$ then the associated hypothesis is rejected, otherwise all hypotheses are retained and no more testing of primary or key secondary hypotheses for the lower doses is performed.

QMD Ref: Worldwide-TMP-ST-005-7.0 Effective: 12Aug2019	Governing QMD: Worldwide-SOP-ST-001		
Confidentiality Statement			
This document is the property of Worldwide Clinical Trials Inc. and may not be duplicated, copied, altered or removed from company without prior approval from Worldwide Quality Assurance or in compliance with Worldwide Standard Operating Procedures.			
phot approval nonit wondwide Quanty Assurance of in compnance with wondwide Standard Operating Proceedings.			
REF Worldwide-TMP-OA-001f-1 3	Page 40 of 49		

Worldwide Clinical Trials Controlled Quality Management Document		

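### With 20 imputations, the pattern-mixture p-value carries avoidable simulation noise when it lies at about 0.04 to 0.05; several hundred would remove most of it at no cost but computing time

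*SAP*

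**What the plan says.** SAP 6.12.4.1 gives the purpose of the analysis: "To assess the robustness of the results to deviations from the MAR assumption in the primary analysis". Imputation has two steps. The first fills intermittent gaps under missing at random (MAR) and is drawn once: "PROC MI DATA=DATAIN OUT=DATAIN_MONO SEED=32641726 NIMPUTE=1". The second imputes the remaining missing values from a model fitted to placebo patients, "with options nimpute = 20 and seed = 32641726". Each completed dataset is analysed with the primary mixed model for repeated measures (MMRM), and the treatment-group means and their "differences between treatments will be combined across all 20 imputed datasets". Inference is "based on the combined estimates using the standard multiple imputation technique via" Rubin's rules. The section then asks for an estimate, standard error and p-value for each week, with Week 12 the timepoint of interest.

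The other MNAR analysis, in SAP 6.12.4.2, is conditional: "If the primary efficacy analysis significantly favours mesdopetam, a tipping-point sensitivity analysis" is done on the significant dose groups. That section states no number of imputations. Neither section gives a reason for choosing 20, a target for Monte Carlo error, or an instruction to report that error.

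**The concern.** A pooled estimate from a finite number of imputations depends partly on the random numbers drawn. With few imputations, the printed p-value can differ noticeably from the value that many imputations would give. That matters little when the result is far from the significance level. Close to it, a reader who compares the sensitivity p-value with 0.05 may be responding to the seed and not to the data. When the primary analysis is not significant, the tipping-point analysis is not run and this is the only MNAR result reported.

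**Working it through.** **Plan's own figure.** Protocol 14.2 assumes a 3 h difference and an SD of 3.5 h, with "92% power and type 1 error rate 0.05 (two tailed"). SAP section 4 takes 31 evaluable patients per group.
- Standard error = 3.5 × √(2/31) = 0.889 h.
- Power = Φ(3/0.889 − 1.96) = Φ(1.415) = 92.1%. The stated 92% is reproduced (91.3% with the noncentral t).
- After the increase to 154 patients there are about 38 per group, and with no missing data the standard error is 3.5 × √(2/38) = 0.803 h.

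The plan's own numbers therefore put the standard error at about 0.8 to 0.9 h.

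**Formula.** Let B be the between-imputation variance, T the total variance and m the number of imputations. Over seeds, the pooled estimate has variance of about B/m. Dividing by T, the test statistic has SD ≈ √(FMI/m), where FMI ≈ B/T is the fraction of missing information. If the long-run p corresponds to z, the chance that the printed p exceeds 0.05 is Φ((1.960 − z)/SD).

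**Assumption.** FMI is not in the documents. I take 0.08 to 0.25. Simulations of placebo-based imputation gave 0.06 to 0.12 with 10% of Week 12 data missing, and 0.10 to 0.25 with 20 to 25% missing. They used 35 or 38 per arm, between-visit correlation 0.5 or 0.7, and ANCOVA at Week 12 in place of the MMRM.

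**Noise in the statistic and in hours.**
- m = 20: √(0.08/20) = 0.063 and √(0.25/20) = 0.112. In hours: 0.063 × 0.8 = 0.05 and 0.112 × 0.9 = 0.10.
- m = 500: 0.013 and 0.022. In hours: 0.01 and 0.02.

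**Chance that the printed p exceeds 0.05** (range over FMI 0.08 to 0.25):

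| Long-run p | z | m = 20 | m = 100 | m = 500 |
|---|---|---|---|---|
| 0.03 | 2.170 | 0.04–3% | 0% | 0% |
| 0.035 | 2.108 | 1–9% | 0–0.2% | 0% |
| 0.04 | 2.054 | 7–20% | 0.05–3% | 0% |
| 0.045 | 2.005 | 24–35% | 6–19% | 0.02–2.3% |

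Example at p = 0.04, m = 20, FMI 0.25: (1.960 − 2.054)/0.112 = −0.84, and Φ(−0.84) = 20%. At a long-run p of exactly 0.05 the chance is 50% for any m.

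**Check by simulation.** The formula ignores noise in the pooled standard error, so it should be slightly low, and it is. With 38 per arm, FMI 0.12 to 0.19 and a long-run p of 0.042 to 0.044, the printed p exceeded 0.05 in 19 to 35% of runs at m = 20, 2 to 12% at m = 100, 0.3 to 4.5% at m = 200 and 0 to 0.8% at m = 500. At a long-run p of about 0.03 and m = 20, it did so in 0.2 to 2% of runs with 10% missing, and in about 3 to 12% with 20 to 25% missing.

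**The case against.** The best defence is that 20 imputations pooled by Rubin's rules are valid. The pooled standard error already allows for a finite number of imputations, and the seed is fixed in advance, so the run is reproducible and cannot be chosen afterwards. The noise is small in hours: even at 1.96 × 0.10 = 0.2 h it is about 12 minutes, against 30-minute diary intervals and the 1-hour change that Protocol 11.2.3.1 treats as meaningful. If the primary analysis is significant, the tipping-point analysis also runs, so a positive claim does not rest on this p-value alone. All of this stands, and it limits the weight of the point. It does not make the Monte Carlo error necessary: a fixed seed makes one arbitrary draw repeatable, not more precise.

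A reader might infer more than the documents support, in three ways.
- **That a p near 0.03 is also likely to change sides.** At the planned 10% missing this happens for only 0.2 to 2% of seeds. The higher simulated rates need 20 to 25% of Week 12 data missing within the full analysis set. SAP section 4 says only that dropout was higher than expected, and SAP 6.1.2 leaves out patients with no valid post-baseline diary, so that level is not established.
- **That the seed decides a formal verdict of robustness.** SAP 6.12.4.1 sets no threshold for this p-value. The explicit stop at loss of significance belongs to the tipping-point analysis.
- **That the confirmatory result is affected.** The hierarchy in SAP 6.15 starts with the primary endpoint ("first the 7.5 mg b.i.d. will be tested at a 5% level on the primary endpoint") and does not include the pattern-mixture result. The primary MMRM involves no imputation and has no simulation noise.

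**Conclusion.** The point holds as a precision improvement to a supportive analysis, not as an error in the primary result. At 20 imputations, a long-run p between about 0.04 and 0.05 can print on either side of 0.05 depending on the seed. The size rests on an assumed FMI of 0.08 to 0.25 and on a normal approximation that the simulations broadly support. If little Week 12 data is missing within the full analysis set, the effect is smaller. No number of imputations settles a result that truly sits at 0.05; a larger number narrows the band in which the seed matters.

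The single draw in the first step is a related gap. Whenever there are intermittent missing diaries, all 20 datasets share one random filling of them, and raising the second number alone would leave that seed dependence in place.

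**What to change.** In SAP 6.12.4.1:
- Raise the final imputations from 20 to several hundred, for example 500, keep the prespecified seed, and change the sentence on combining 20 datasets to match. One hundred would be enough for a p near 0.03 but leaves 2 to 12% at a p of 0.042 to 0.044 in the simulations.
- Draw the first step the same number of times instead of once, then make one final imputation from each draw.
- Report the Monte Carlo standard error of the pooled difference, √(B/m), beside the p-value.

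In SAP 6.12.4.2, state the same number of imputations, since none is given.

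The cost is a few lines of text and code and more computing time. No data, visits or patients are affected.

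### SAP 6.12.4.1 fills intermittent diary gaps once before drawing 20 control-based imputations, so the Week 4 and Week 8 standard errors in that sensitivity analysis are somewhat too small; Week 12 is barely affected

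*SAP*

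**What the plan says.** SAP 6.12.4.1 introduces its program with the words "The following is the sample SAS code that will be used to implement the control-based pattern mixture imputation", so the code is the planned implementation. It runs as follows.

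- Step 1 fills the non-monotone gaps under MAR, separately by treatment group: "MCMC CHAIN=MULTIPLE IMPUTE=MONOTONE PRIOR = JEFFREYS". It is called with "PROC MI DATA=DATAIN OUT=DATAIN_MONO SEED=32641726 NIMPUTE=1" and writes one dataset, DATAIN_MONO.
- Step 2 applies the placebo-based regression imputation to that dataset: "PROC MI DATA= DATAIN_MONO SEED=32641726 NIMPUTE=20". It has no BY statement on an imputation number.
- Step 3 fits the primary MMRM to each completed dataset. The LS means and differences "will be combined across all 20 imputed datasets", and the inference is said to rest on "combined estimates using the standard multiple imputation technique via Rubin's" rules.

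The prose agrees with the code. It attaches the count of 20 to the second step only: "option MODEL of SAS' PROC MI with options nimpute = 20 and seed = 32641726". Nothing elsewhere in the SAP repeats step 1 or adds its variance. The section closes by promising an SE and p-value for the treatment difference at every week, with Week 12 the week of main interest.

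**The concern.** Rubin's rules measure missing-data uncertainty by how far the results differ between completed datasets. A value drawn once and carried into all 20 datasets does not differ between them, so the pooling treats it as if the patient had recorded it. Every intermittent gap is handled this way.

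Two things follow for the visits where such gaps occur. Their SEs and p-values omit a component that the text promises to include, and their estimates depend on one random draw. The analysis matters because it is the MNAR check that runs whatever the primary result; the tipping-point analysis in SAP 6.12.4.2 is done only after a significant primary test.

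**Working it through.** **Which visits are exposed.** A missing Visit 5 has no later visit, so it is monotone by definition and is imputed in step 2. Step 1 can only fill Visits 3 and 4. SAP 6.1.2 requires at least one valid post-baseline diary for the FAS, so a missing Visit 3 in a FAS patient always has a later observed visit and is always a step 1 fill. Step 1 reaches Week 12 only indirectly, as a predictor in step 2 and through shared MMRM parameters.

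**The plan's own figure.** The documents state nothing about the imputation SE. The design inputs do reproduce: difference 3 h and SD 3.5 (protocol 14.2), with 31 evaluable per group (SAP 4).

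3 / (3.5 × √(2/31)) − 1.96 = 3.375 − 1.96 = 1.415, giving power 92.1% against 92% stated. And 31 / 0.90 = 34.4, so 35 per group.

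**Inputs to the simulation.**

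- From the documents: four equal arms of 38 (154/4 = 38.5) and a change SD of about 3.5 (visit SD 3.9 with correlation 0.6: 3.9 × √(2 × 0.4) = 3.49).
- Assumed: between-visit correlation 0.6; intermittent gaps at 0-20% of Visits 3 and 4; dropout 15%, with 25% as a check; true effects of 1, 2 and 3 h. SAP 4 planned 10% dropout and says the actual rate was higher, without giving it.
- Analysis: unstructured repeated-measures model with baseline and stratum, country omitted, 120 simulated trials per row.

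**Comparison.** (A) One step 1 fill followed by 20 step 2 draws, as in the SAP. (B) Twenty step 1 fills with one step 2 draw each. Both are pooled by T = W + (1 + 1/20) × B, where W is the within- and B the between-imputation variance, and SE = √T.

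Ratio of SEs, A/B, for 7.5 mg versus placebo:

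| Gap rate | Dropout | Week 4 | Week 8 | Week 12 |
|---|---|---|---|---|
| 0% | 15% | 1.000 | 1.003 | 0.999 |
| 2% | 15% | 0.993 | 0.991 | 0.991 |
| 5% | 15% | 0.980 | 0.985 | 0.996 |
| 10% | 15% | 0.961 | 0.965 | 0.991 |
| 20% | 15% | 0.911 | 0.916 | 0.997 |
| 10% | 25% | 0.964 | 0.963 | 0.993 |

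**One cell in full (10% gaps, 15% dropout, Week 4).** B is 0.0003 under the SAP code and 0.0429 with 20 fills. Total variance is 0.7286² = 0.5309 against 0.7579² = 0.5744. The difference of 0.0435 is close to 1.05 × (0.0429 − 0.0003) = 0.0447, so the shortfall is the lost between-imputation term. Ratio: √(0.5309/0.5744) = 0.961.

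**In hours.** A normal 95% half-width at Week 4 is too short by 1.96 × (0.7579 − 0.7286) = 0.06 h with 10% gaps and 1.96 × (0.8136 − 0.7410) = 0.14 h with 20%. At Week 12 with 10% gaps it is 1.96 × (0.8119 − 0.8046) = 0.01 h.

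**Dependence on one draw.** At Week 4 with 10% gaps, the estimate from a single fill varies between seeds with an SD of about √0.0429 = 0.21 h. Averaging 20 fills reduces this to √(0.0429/20) = 0.05 h.

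**Against the actual spread of the estimates.** An SD from 120 trials has a relative error of about 1/√(2 × 119) = 6.5%. With 20% gaps, the SAP code's SEs at Weeks 4 and 8 (0.741, 0.781) are below the empirical SDs (0.923, 0.877); with 20 fills they are 0.814 and 0.852 against 0.851 and 0.828. At Week 12 the SAP code's SE (about 0.80) is above the empirical SD (0.62-0.76 at 15% dropout).

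**The case against.** The strongest reply is that nothing of consequence rests on the affected figures. Week 12 is the timepoint of interest, step 1 never fills it, and the shortfall there is within simulation noise. The testing hierarchy in SAP 6.15 covers the primary and key secondary tests, and no decision rule is attached to this sensitivity analysis. Gaps may also be few: under SAP 6.2.12.2 one valid diary of three is enough for a visit, and sites telephone patients before and after each diary period. With no gaps there is no effect. All of this stands, and it limits the weight of the point. It does not make the code do what the text promises, and the Week 4 and Week 8 results will be tabulated with SEs and p-values.

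A reader might infer more than the documents support:

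- *That every SE in the analysis, including Week 12, is too narrow.* The Week 12 ratio is 0.991 or higher, and the Week 12 SE exceeds the empirical SD, as expected when active-arm dropouts borrow from placebo. Too small here means relative to Rubin's rules over both steps.
- *That the single fill contradicts the SAP's description of the analysis as conservative.* That word describes the treatment-effect estimate, which is conservative because active-arm dropouts are imputed from placebo. It makes no claim about the SE.
- *That the treatment-variable mismatch biases the result.* Step 2 declares TRT01PN in CLASS but refers to "MODELOBS=(TRT01P='Placebo", a variable the SAP does not define. This is a clerical slip in sample code, and the independent double programming in SAP 6.3.3 should expose it.

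**Conclusion.** The point holds as a minor correction to one sensitivity analysis. As written, the pooling omits the uncertainty of the intermittent fills; that follows from the code and needs no simulation. The size depends on the gap rate: at Weeks 4 and 8 the SE of the treatment difference is too small by about 0% with no gaps, 1% with 2%, 2% with 5%, 4% with 10% and 8-9% with 20%. At Week 12 it is at most about 1% and unlikely to alter the conclusion. These figures rest on assumed gap rates, correlation 0.6 and 15% dropout; raising dropout to 25% at the 10% gap rate hardly changed them. The primary MMRM is untouched.

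**What to change.** In SAP 6.12.4.1:

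1. Set NIMPUTE=20 in the first PROC MI.
2. Sort its output by _IMPUTATION_. The sort is needed because step 1 runs by treatment group, so its output is ordered by arm first.
3. Run the second PROC MI with NIMPUTE=1 and BY _IMPUTATION_.
4. Fit the MMRM to each of the 20 datasets and pool as now planned.
5. Amend the sentence that ties the count of 20 to the MNAR step, so that text and code agree.
6. While editing, use one treatment variable in both CLASS and MODELOBS.

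The cost is a few lines of code and text, and slightly wider Week 4 and Week 8 SEs in this sensitivity analysis. It needs no new data and no change to the design or the primary analysis.
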